20.5 Urgent safety measures

The Sponsor or Investigator may take appropriate urgent safety measures to protect study participants from any immediate hazard to their health or safety. Urgent safety measures may be taken without prior authorisation. The study may continue with the urgent safety measures in place. **The Investigator must inform the Trial Office IMMEDIATELY if the study site initiates an urgent safety measure:**

The notification must include:

- Date of the urgent safety measure;
- Who took the decision; and
- Why the action was taken.

The Investigator will provide any other information that may be required to enable the Trial Office to report and manage the urgent safety measure in accordance with the current ethical requirements for expedited reporting. The Trial Office will follow written procedures to implement the changes accordingly.

20.6 Temporary halt

The Sponsor and Investigators reserve the right to place recruitment to this protocol on hold for short periods for administrative reasons **or** to declare a temporary halt. A temporary halt is defined as a formal decision to:

- Interrupt the treatment of subjects already in the study for safety reasons;
- Stop recruitment on safety grounds; or
- Stop recruitment for any other reason(s) considered to meet the substantial amendment criteria, including possible impact on the feasibility of completing the study in a timely manner.

The Trial Office will report the temporary halt via an expedited substantial amendment procedure to the REC. The study may not restart after a temporary halt until a further substantial amendment to re-open is in place. If it is decided not to restart the study this will be reported as an early termination.

20.7 Serious Breaches

Investigators must notify the Trial Office at once if any serious breach of GCP is suspected. A serious breach is defined as "A breach of GCP or the study protocol which is likely to effect to a significant degree:

- The safety or physical or mental integrity of the subjects of the study; or
- The scientific value of the study"

The Trial Office will review the event and, if appropriate a report will be submitted to the Sponsor office and to the REC, where appropriate within 7 days of the Trial Office becoming aware of the breach, as per OCTRU SOPs.

20.8 Trial Reports

This protocol will comply with all current applicable Research Ethics Committee, Health Research Authority, Medicines and Healthcare products Regulatory Agency and Sponsor requirements for the provision of periodic study safety and progress reports. Any additional reports will be provided on request. Reporting will be managed by the Trial Office according to internal SOPs. Sites will be urged to return as much data as possible before each database lock point.

The Trial Office will determine which reports need to be circulated to Principal Investigators and other interested parties according to internal SOPs. Study teams at sites are responsible for forwarding study reports they receive to their local Trust as required.

21 EXPENSES AND BENEFITS

The study sites may provide reasonable patient travel expenses as per local practice. There is no specific funding within the budget of this study for expenses.

22 QUALITY ASSURANCE

22.1 Risk assessment

A risk assessment and a monitoring plan will be prepared before the study opens. The risk assessment will be repeated if necessary in the light of changes while the study is ongoing or in response to monitoring reports. Monitoring plans will be amended as appropriate.

22.2 Monitoring

Monitoring will be performed according to the monitoring plan. Data will be evaluated for compliance with the protocol and accuracy in relation to source documents. The investigator and institutions involved in the study will permit study-related monitoring and provide direct access to all study records and facilities. They will provide adequate time and space for the completion of monitoring activities.

The study site will be monitored centrally by checking incoming data for compliance with the protocol, consistency, completeness and timing. The case report data will be validated using appropriate set criteria, range and verification checks. The study site must resolve all data queries in a timely manner. All queries relating to key outcome and safety data and any requiring further clarification will be referred back to the study site for resolution. For other non-critical data items, OCTO staff may resolve data queries centrally providing the correct answer is clear. Such changes will be clearly identified in the eCRF and the study site informed.

The study site will also be monitored by site visit as necessary to ensure their proper conduct of the study. OCTO staff will be in regular contact with site personnel to check on progress and deal with any queries that they may have.

All patient personal identifiers must be obliterated from the information except where explicit consent for release of personal information has been obtained from the patient. The study site will provide copies of the following participant information to the Trial Office on request for remote monitoring purposes:

- Participant screening log

22.3 Audits

All aspects of the study conduct may be subject to internal or external quality assurance audit to ensure compliance with the protocol, GCP requirements and other applicable regulation or standards. It may also be subject to a regulatory inspection. Such audits may occur at any time during or after the completion of the study. Investigators and their host Institution(s) should understand that it is necessary to allow auditors direct access to all relevant documents, study facilities and to allocate their time and the time of their staff to facilitate the audit or inspection visit. Anyone receiving notification of a Regulatory Inspection that will (or is likely to) involve this trial must inform the Trial Office without delay.

23 RECORDS RETENTION & ARCHIVING

During the clinical study and after study closure the Investigator must maintain adequate and accurate records to enable the conduct of a clinical study and the quality of the research data to be evaluated and verified. All essential documents must be stored in such a way that ensures that they are readily available, upon request for the minimum period required by national legislation or for longer if needed. It is the University of Oxford's policy to store data for a minimum of 5 years. Investigators may not archive or destroy study essential documents or samples without written instruction from the Trial Office. The medical files of study participants shall be retained in accordance with national legislation and in accordance with the host institution policy.

Retention and storage of laboratory records for clinical study samples must also follow these guidelines.

Retention and storage of central laboratory records supporting the endpoints of the study and the disposition of samples donated via the study must also comply with applicable legislation and Sponsor requirements.

24 PATIENT CONFIDENTIALITY

Personal data recorded on all documents will be regarded as confidential, and to preserve each patient's anonymity, only their month and year of birth will be recorded on the eCRF. The study will comply with the Data Protection Act, which requires data to be anonymised as soon as it is practical to do so.

The Investigator site must maintain the patient's anonymity in all communications and reports related to the research. The Investigator site team must keep a separate log of enrolled patients' personal identification details as necessary to enable them to be tracked. These documents must be retained securely, in strict confidence. They form part of the Investigator Site File and are not to be released externally.

Anonymised data may be used in future research, including by other organisations in the UK and overseas and the commercial sector.

The Sponsor or delegate will act as Data Custodian for the trial.

25 STUDY FUNDING

This study is funded by Cancer Research UK (Population Research Committee ref A22173) and supported by the CRUK Oxford Centre (formerly the Oxford Cancer Research Centre) and the CRUK/MRC Oxford Institute for Radiation Oncology. The Cytosponge™ devices are kindly supplied by Cambridge University Hospitals. The trial will be NIHR adopted. There will be no funding available to the study sites for NHS excess treatment costs.

26 SPONSORSHIP AND INDEMNITY

26.1 Sponsorship

The Sponsor will provide written confirmation of Sponsorship and authorise the study commencement once satisfied that all arrangements and approvals for the proper conduct of the study are in place. A separate study delegation agreement, setting out the responsibilities of the Chief Investigator and Sponsor will be put in place between the parties.

26.2 Indemnity

The University has a specialist insurance policy in place which would operate in the event of any participant suffering harm as a result of their involvement in the research (Newline Underwriting Management Ltd, at Lloyd's of London, policy numbered: WD1200463). Product liability insurance will be provided by the legal manufacturer of the Cytosponge™ device.

NHS indemnity operates in respect of the clinical treatment, which is provided.

26.3 Contracts/Agreements

This study is subject to the Sponsor's policy requiring that written contracts/agreements are agreed formally by the participating bodies as appropriate. A Clinical Trial Agreement (CTA) will be placed between the Sponsor and participating NHS Trusts prior to site activation.

The Sponsor will also set up written agreements with any other external third parties involved in the conduct of the study as appropriate.

27 PUBLICATION POLICY

The intention is to publish this research in a specialist peer reviewed scientific journal on completion of the study. The results may also be presented at scientific meetings and/or used for a thesis. No study results may be published or presented without the prior approval of the TMG. The Investigators will be involved in reviewing drafts of the manuscripts, abstracts, press releases and any other publications arising from the study. Authorship will be determined in accordance with the ICMJE guidelines and other contributors will be acknowledged. Authors will ensure the current Department of Oncology publications acknowledgement statement is inserted. Authors will acknowledge that the study was sponsored by the University of Oxford.

29 WHO PERFORMANCE STATUS

Grade	Explanation of activity
0	Fully active, able to carry on all pre-disease performance without restriction
1	Restricted in physically strenuous activity but ambulatory and able to carry out work of a light or sedentary nature, e.g., light house work, office work
2	Ambulatory and capable of all self-care but unable to carry out any work activities. Up and about more than 50% of waking hours
3	Capable of only limited self-care, confined to bed or chair more than 50% of waking hours
4	Completely disabled. Cannot carry out any self-care. Totally confined to bed or chair

30 APPENDIX 1: AMENDMENT HISTORY

Amendment No.	Protocol Version No.	Date issued	Author(s) of changes	Details of Changes made
001	2.0	22Jan2018	[name]	
Section 24 Patient Confidentiality:
 
 - Data collection on CRF changed from initials and date of birth to month and year of birth at request of REC. - [name] [name] role changed. 
Approved by the REC during their initial approval. Changes only submitted to the MHRA as an amendment.

002	3.0	20Feb2019	[name]	Clarification of a minor typographical error in Protocol exclusion criteria number 1 listed in Protocol Synopsis & Section 4.2

## 1. INTRODUCTION

This document details the proposed data presentation and analysis for the main paper(s) and final study reports from the ***Evaluation of a Non-Endoscopic Immunocytological Device (Cytosponge™) for post chemo-radiotherapy surveillance in patients with oesophageal cancer – a feasibility study***. The results reported in these papers should follow the strategy set out here. Subsequent analyses of a more exploratory nature will not be bound by this strategy, though they are expected to follow the broad principles laid down here. The principles are not intended to curtail exploratory analysis (for example, to decide cut-points for categorisation of continuous variables), nor to prohibit accepted practices (for example, data transformation prior to analysis), but they are intended to establish the rules that will be followed, as closely as possible, when analysing and reporting the trial.

The analysis strategy will be available on request when the principal papers are submitted for publication in a journal. Suggestions for subsequent analyses by journal editors or referees, will be considered carefully, and carried out as far as possible in line with the principles of this analysis strategy; if reported, the source of the suggestion will be acknowledged.

Any deviations from the statistical analysis plan will be described and justified in the final report of the trial. The analysis should be carried out by an identified, appropriately qualified and experienced statistician, who should ensure the integrity of the data during their processing. Examples of such procedures include quality control and evaluation procedures.

**1.2 Changes from previous version of SAP**

A summary of key changes from earlier versions of SAP, with particular relevance to protocol changes that have an impact on the design, definition, sample size, data quality/collection and analysis of the outcomes will be provided. Include protocol version number and date.

Version number Issue date	Author of this issue	Protocol Version & Issue date	Significant changes from previous version together with reasons
V1.0_22Apr2020	HO	Protocol_3.0_20Feb2019	Not applicable as this is the 1 st issue

## 2. BACKGROUND AND OBJECTIVES

### 2.1 Background and rationale

There are around 8900 new cases of oesophageal cancer in the UK every year and the UK incidence rate is the second highest in Europe for males and the highest for females (CRUK Cancer Statistics, 2013-2015). Surgery is often challenging in oesophageal cancer patients and a non-surgical approach, i.e. definitive chemoradiotherapy (dCRT), may be the preferred treatment, reserving surgery for salvage. Although overall survival in patients treated with dCRT remains comparable to those treated with surgical-based therapy (Stahl et al, 2005), the higher incidence of loco-regional recurrence and the lack of an effective surveillance strategy have deterred many clinicians from adopting dCRT plus salvage surgery as the standard approach. Regular endoscopic surveillance is invasive; this study will investigate the feasibility of a less invasive technique, Cytosponge™, in post CRT surveillance in oesophageal cancer. If found to be feasible, it will lead to larger studies evaluating the role of Cytosponge™ in surveillance post-dCRT. An effective surveillance programme may detect a greater proportion of patients with local-only recurrences treatable by curative salvage resection. It may also lead to a shift in standard care where patients could be offered dCRT as first choice, keeping surgery in reserve for patients who fail dCRT.

There are no Investigational Medicinal Products (IMPs) in this trial. The only study-specific interventional procedure is the investigational Cytosponge™ procedure, which will comply with the MHRA Medical Device Directive. The Cytosponge™ is supplied by Cambridge University Hospital, the legal manufacturer of the device. The Cytosponge™ is not CE marked and not authorised for use in the UK. The trial will be conducted under a Notification of No Objection from the MHRA.

Cytosponge™ test kit, is a Class I, single-use, non-sterile, non CE-marked device that consists of an expandable spherical 3cm diameter mesh, encapsulated in a gelatine capsule, which is attached to a cord. The capsule is swallowed and allowed to reach the stomach while remaining attached to the cord, which is held onto by the patient or a qualified member of the trial team. 3-5 minutes after swallowing (once dissolved in the stomach) the spherical mesh can be retrieved by pulling on the cord. Cells are collected by the mesh scraping against the oesophageal mucosa.

## 2.2 Objectives

Primary Objective	Endpoint
Completion rate	The proportion of consented, evaluable, patients successfully undergoing Cytosponge™ will be presented, with the corresponding 95% confidence interval. The proportion will be calculated overall and separately for those having dCRT and naCRT.
Secondary Objectives	Endpoints
Safety	All serious adverse effects related to the procedure, including bleeding (requiring transfusion) and perforation.
Suitability of sample for biomarker analysis	Quality of material obtained from Cytosponge™ test will be centrally analysed at Cambridge (cellularity, yield and quality of extracted DNA will be used as measure of quality). A positive Cytosponge™ result will be defined as presence of cytological atypia and/or p53 mutation
Acceptance rate	
 
1. Proportion of eligible patients approached who consent
 
2. Proportion of patients who have successfully undergone the procedure & would be prepared to accept the procedure repeatedly if it was to be used for follow-up (data will be captured through questionnaire after procedure)
 

Tertiary Objectives	Endpoints
Residual disease markers	Level of ctDNA in responders vs non-responders
Cytosponge™ comparative efficacy to biopsy	Level of residual cancer, p53 mutations & other identifiable markers in Cytosponge™, pre & post- treatment biopsies

## 3. STUDY METHODS

### 3.1 Trial Design/framework

CYTOFLOC is a feasibility study testing the use of the Cytosponge™ to determine completion rate, safety and acceptability of the procedure. The Cytosponge™ is a non-CE-marked, single-use, non-sterile, 3cm diameter, polyester, medical grade sphere on a string, compressed within a capsule. The capsule is swallowed and allowed to reach the stomach while remaining attached to the cord, which is held onto by the patient or a qualified member of the trial team. Three to five minutes after swallowing (once dissolved in the stomach) the spherical mesh can be retrieved by pulling on the cord.

Fifty patients will be recruited from approximately 10 sites in the UK.

Patients will receive one Cytosponge™ test at one time-point 4 to 16 weeks after completion of CRT (either dCRT or naCRT). Patients will be in the study for about a month in total, from entry until the last protocol visit.

Trial Open (start of recruitment):	13Apr2018
End of recruitment:	31Jan2020
Date expected end follow-up/start of data cleaning:	28Feb2020
Expected start of final analysis:	16Mar2020

### 3.2 Randomisation and Blinding

Not applicable: this is not a randomised study.

### 3.3 Sample Size

The trial aims to recruit 50 evaluable patients in 24 months from approximately 10 UK centres to give a completion rate estimate to +/-13% for feasibility (asymptotic 95% CI, estimated 70% rate) and enough samples to consider markers. Participants that do not receive the intervention will be withdrawn and replaced at the Chief Investigator's discretion.

### 3.4 Statistical Interim Analysis, Data Review and Stopping guidelines

There is no independent Data and Safety Monitoring Committee (DSMC) established for this study, a study oversight and trial conduct review will be provided by the independent Radiotherapy and Imaging Trial Oversight Committee (RIOC). The RIOC has three independent members and meets every six months, and its role includes providing oversight, monitoring completeness of data, and monitoring evidence for treatment harm. Further details are given in the RIOC Charter (which is held by the trial management team).

No formal interim analysis is planned. There is a stopping rule: the study will be stopped if there is more than one serious life-threatening complication from the Cytosponge™ (e.g. oesophageal perforation or life-threatening gastro-intestinal bleeding). Within the remit of the Trial Management Group (TMG) is a discussion of any safety issues. The TMG will report any such complications to the RIOC.

### 3.5 Timing of Final Analysis

All primary and secondary feasibility outcomes will be collectively assessed i.e. assessed at the same time point. Tertiary outcomes will be analysed at the same time, if available or separately at a later date.

### 3.6 Blinded analysis

Not applicable.

### 3.7 Statistical Analysis Outline (as in Protocol)

The completion rate (swallowing of the sponge, retrieval of the sponge without additional intervention) with corresponding 95% confidence interval will be calculated at the end of the trial. Results will be given for all patients and also separately for (1) patients recruited post-dCRT and (2) patients recruited post-naCRT.

**Stopping rules:** The study will be stopped if there is more than one serious life-threatening complication from the Cytosponge™ (e.g. oesophageal perforation or life-threatening gastro-intestinal bleeding).

A statistical analysis plan will be finalised before release of the final data set.

#### Inclusion in analysis

To be evaluable for assessment of the study primary endpoint, participants must have attempted to swallow the Cytosponge™.

#### Subgroup analysis

The primary endpoint, the completion rate, will be calculated overall and separately for those having Definitive Chemoradiotherapy (dCRT) and Neo-adjuvant Chemoradiotherapy (naCRT).

## Interim Analyses

No formal interim analysis of results is planned for this study.

## Procedures for reporting any deviation(s) from the original statistical plan

Any deviations from the original statistical plan will be described and justified in the final report.

## Final analysis

Final analysis will be after end of study evaluations have been recorded and data has been checked to be complete and accurate. Decision to proceed to a formal phase II will be determined by whether the primary and secondary objectives of this study have been met. If the completion rate is >70% then the trial outcome will be to develop a randomised phase II/ III study testing Cytosponge™ in post-CRT follow-up.

## 4. STATISTICAL PRINCIPLES

### 4.1 Statistical Significance and Multiple Testing

A 5% significance level (corresponding to two-sided hypothesis tests) and 95% confidence intervals will be reported. No adjustments will be made for multiple testing as this is a feasibility study.

### 4.2 Definition of Analysis Populations

**Population for assessment of completion rate:** all patients who have provided consent and have attempted to swallow the Cytosponge™.

**Population for calculation of consent rate:** all patients who consented, out of all those patients who were eligible.

**Population for assessment of acceptance rate:** all patients who successfully undergo the Cytosponge™ procedure.

[figure not shown]
**Population for assessment of suitability of sample:** all samples (taken during the Cytosponge™ procedure) sent to Cambridge for analysis.

**Safety population:** all participants who attempted to swallow the Cytosponge™.

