7.2 Samples to be sent to and analysed in a Central Laboratory

All Cytosponge™ specimens will be couriered to the [name] Laboratory, at the MRC Cancer Unit. Cytosponge™ specimens will be processed in conjunction with the Cambridge University Hospitals' NHS Foundation Trust tissue bank which is accredited to GLP standards [10]. Samples will be processed to a paraffin embedded cell clot, sectioned and stained with Haematoxylin and Eosin (2 levels) and for immunohistochemical markers (TFF3 if adenocarcinoma, p53 in all cases) using a DAKO autostainer according to GCP standards. An expert GI cytologist will verify any atypia and positive immunostaining. In addition, DNA will be extracted for p53 sequencing using a multiplex assay as previously described and for ploidy status. Although timely processing will ensure that the study completes on time the results of Cytosponge™ samples will not affect patient clinical care since it is not being used as a diagnostic tool in the trial, and therefore there is some flexibility in the timeline. The biomarkers will be scored according to previously optimised protocols [10, 13-15]. These data will be compared to the degree of dysplasia determined from endoscopic biopsies or surgical specimen where surplus material is available as a result of routine care procedures. For further details, please refer to the Device & Sample Handling Manual.

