13 STATISTICAL CONSIDERATIONS

13.1 Sample size and power

The trial aims is to recruit 50 evaluable patients in 24 months from approximately 10 UK centres to give a completion rate estimate to +/-13% for feasibility (95% CI, estimated 70% rate) and enough samples to consider markers. Participants that do not receive the intervention will be withdrawn and replaced at the Chief Investigator’s discretion.

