14.5 Final analysis

Final analysis will be after end of study evaluations have been recorded and data has been checked to be complete and accurate. Decision to proceed to a formal phase II will be determined by whether the primary and secondary objectives of this study have been met. If the completion rate is >70% then the trial outcome will be to develop a randomised phase II/ III testing Cytosponge™ in post-CRT follow-up.

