## 6. ANALYSIS

### 6.1 Definitions of feasibility outcomes

#### 6.1.1 Primary feasibility outcome

The primary outcome measure is the completion rate, defined as the proportion of consented, evaluable participants who are able to successfully undergo the Cytosponge™ procedure. i.e. patients who are able to swallow the sponge and have the sponge retrieved without additional intervention. Evaluable participants are those who have attempted to swallow the Cytosponge™.

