#### 6.1.2 Secondary feasibility outcomes

**Safety:** defined as all serious adverse events (including bleeding requiring transfusion and perforation) that occur between from the time of Cytosponge™ administration (D1) and when the patient completes the study at the two week telephone follow-up. If a participant undergoes surgery prior to their two week follow up visit, then their safety reporting period continues until the time of surgery. Adverse events will also be reported. Severity rating of adverse effects will be as per the Common Terminology Criteria for Adverse Events (CTCAE) V4.03.

**Consent rate:** defined as the proportion of eligible patients who consent to take part in the study.

**Acceptance rate:** defined as the proportion of patients who have successfully undergone the Cytosponge™ procedure and would be prepared to accept the procedure repeatedly if it was to be used for follow-up.

**Suitability of sample for biomarker analysis:** defined as the percentage of samples from the Cytosponge™ test with the presence of cytological atypia and/or p53 abnormality (also called “positive samples”).

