**Acceptance rate** (acceptance to repeat procedure), defined as the percentage of patients who have successfully undergone the Cytosponge™ procedure and would be prepared to accept the procedure repeatedly if it was to be used for follow-up. A questionnaire will be given to each patient, to be completed after the procedure. The questionnaire will either be completed just after the procedure or, if the patient cannot stay, completed later and returned by post.

**Suitability of sample for biomarker analysis**, defined as the percentage of samples from the Cytosponge™ test with the presence of cytological atypia and/or p53 abnormality (also called “positive samples”). Quality of material obtained from the Cytosponge™ test will be centrally analysed at Cambridge. Cellularity, yield and quality of extracted DNA will be used as measure of quality. Data for these analyses are not expected to be available with the data for the primary outcome and the acceptance- and safety-related secondary outcomes; biomarker analyses will therefore be conducted and reported separately.

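### Sample suitability is measured per sample sent, so no planned figure gives the proportion of patients attempting the test who end with an adequate sample

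*SAP*

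**What the plan says.** SAP 4.2 gives each outcome its own population. For completion it is "all patients who have provided consent and have attempted to swallow the Cytosponge™", and the safety population is likewise everyone who attempted the swallow. For sample suitability it is "all samples (taken during the Cytosponge™ procedure) sent to Cambridge for analysis".

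The numerators also differ. SAP 6.1.1 counts as completions "patients who are able to swallow the sponge and have the sponge retrieved without additional intervention". SAP 6.1.2 has suitability "defined as the percentage of samples from the Cytosponge™ test with the presence of cytological atypia and/or p53 abnormality", which is a positivity rate. SAP 6.2.2 then adds: "Cellularity, yield and quality of extracted DNA will be used as measure of quality". It gives no threshold, denominator or summary statistic for these measures, and it expects the biomarker results to be reported apart from the primary outcome.

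Protocol 7.2 says "All Cytosponge™ specimens will be couriered to the" central laboratory, so every retrieved specimen is meant to be sent. Protocol 13.1 justifies the 50 patients partly by "enough samples to consider markers", without a number. Protocol 14.5 states: "Decision to proceed to a formal phase II will be determined by whether the primary and secondary objectives of this study have been met". The only numerical criterion there is a completion rate above 70%.

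**The concern.** A surveillance test is useful only when an attempt ends with material that the laboratory can analyse. Protocol 1.3 names two ways in which these patients may differ from Barrett's patients: dysphagia may hinder swallowing or retrieval, and radiation inflammation may complicate sample analysis. The first loses patients before the laboratory and the second loses information in it. A patient can be lost at either step, so the natural feasibility quantity covers both.

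The plan measures the steps on different populations and reports them at different times. A reader of the final reports would have a completion percentage per attempter and a laboratory percentage per sample sent, with no planned figure joining them. At stake are the secondary-objective part of the decision to proceed and the planning of a later trial, which needs to know how many attempts give one usable result.

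**Working it through.** **Step 1: the plan's own precision figure.** SAP 3.3 gives n = 50, an expected rate of 70%, an asymptotic 95% CI and a precision of ±13%.

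Half-width = 1.96 × √(0.70 × 0.30 / 50) = 0.127, which rounds to 13%. Conversely, n = 1.96² × 0.21 / 0.13² = 47.7, so 48 patients would give exactly that precision. The figure reproduces and is not disputed. It concerns completion only; no precision is stated for sample yield.

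**Step 2: where each kind of attempt is counted.**

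| Outcome of an attempt | Completion rate | Suitability population |
|---|---|---|
| Swallow fails | failure | outside |
| Swallowed, no specimen obtained | failure | outside |
| Retrieved with extra intervention, sample sent | failure | inside |
| Completed, sample not sent | success | outside |
| Completed, sample sent | success | inside |

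The two populations are not nested: the third row is a failure in one and a member of the other.

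**Step 3: size of the denominator effect.** Let N be attempts, S samples sent and A adequate samples. The per-sample rate is A/S and the per-attempt rate is A/N, so their ratio is N/S whatever A is.

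Assumptions: only completers yield a sample, and all of those samples are sent. The documents give no adequacy rate, so about 80% to 100% of sent samples is assumed. Intervals are exact (Clopper-Pearson) 95%.

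| Completers of 50 | Adequate | Per sample | Per attempt | Ratio |
|---|---|---|---|---|
| 35 (70%) | 28 | 80.0% (63.1 to 91.6) | 56% (41.3 to 70.0) | 50/35 = 1.43 |
| 35 (70%) | 32 | 91.4% (76.9 to 98.2) | 64% (49.2 to 77.1) | 1.43 |
| 35 (70%) | 35 | 100% (90.0 to 100) | 70% (55.4 to 82.1) | 1.43 |
| 45 (90%) | 36 | 80.0% (65.4 to 90.4) | 72% (57.5 to 83.8) | 50/45 = 1.11 |
| 48 (96%) | 43 | 89.6% (77.3 to 96.5) | 86% (73.3 to 94.2) | 50/48 = 1.04 |

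**Step 4: can the yield be rebuilt by multiplying the two planned rates?** No, for two reasons.

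- *The numerator is positivity.* A cellular sample with good DNA and no abnormality is adequate but not positive. Protocol 1.1 cites complete pathological response in 25% to 49% of cases, so adequate negative samples are to be expected.
- *Rescued sponges break the chain.* Suppose 35 of 50 complete and 5 more sponges are retrieved with extra intervention and sent. Then S = 40. If 32 are adequate, the per-sample rate is 32/40 = 80% and the product is 0.70 × 0.80 = 56%, but the true per-attempt yield is 32/50 = 64%. The 5 is hypothetical and serves only to show that the product can be wrong.

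**The case against.** The strongest reply is that the failures are already counted. Completion covers both swallowing and retrieval, has all attempters as its denominator, comes with a 95% CI, and carries the only numerical go criterion. A reader might infer that failed swallows and unretrieved sponges vanish from the analysis, or that the suitability percentage could hide them from the decision. The documents do not support that: each such attempt lowers the completion rate. Nor do they support a large planned loss between retrieval and dispatch, since Protocol 7.2 has all specimens couriered and SAP 6.3 says missing data will be described.

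A reader might also infer that the plan will print an inflated percentage of usable samples, such as the 80% above. It will not, because the SAP's percentage is of positive samples and no usable-sample percentage is defined on any denominator. For the same reason, changing the denominator alone would not help. Positives divided by all attempters would treat a failed swallow as a non-positive result, which is not a yield.

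It is also fair to say that samples are the natural denominator for quality of material, and that reporting each step on its own population is coherent in a 50-patient feasibility study. The effect may be small: Protocol 1.3 cites 96.5% completion in squamous dysplasia, although in a different population. Finally, a figure in SAP 4.2 is not shown and SAP 5.1 has no text in the copy reviewed, so a flow chart with sample counts may exist. Counts would help, but they would not by themselves prespecify the proportion, its interval or what counts as adequate.

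What remains is that no readable passage plans the per-attempt yield, and that it cannot be derived from the two percentages that are planned.

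**Conclusion.** The concern holds as a reporting gap, not as a bias in the primary endpoint. Attempts without a specimen lie outside the suitability population and appear only as completion failures. The proportion of attempting patients who end with an adequate sample is neither planned nor recoverable from the planned rates.

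At the plan's own 70% completion assumption, a per-sample adequacy rate would be 1.43 times the per-attempt rate, for example 80% against 56%; at 48/50 completion it would be 1.04 times. These ratios assume that only completers yield samples and that all their samples are sent. The adequacy rates are illustrative. The gap bears on the feasibility question and on the secondary-objective part of the decision to proceed. It does not affect the completion criterion of more than 70%.

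**What to change.** In SAP 4.2 and 6.2.2:

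- Keep the per-sample figure and label it as laboratory performance.
- Add the proportion of all patients who attempted the swallow who end with an adequate sample, with a 95% CI. Count no sample, not sent, lost and inadequate as not adequate.
- Define adequacy from the measures that SAP 6.2.2 already names (cellularity, DNA yield and DNA quality). The laboratory should set the thresholds before the results are examined.
- Report positivity separately.
- Give the counts attempted, retrieved, sent and adequate, so that each loss can be seen.

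The cost is SAP wording, one extra table row, agreement on adequacy thresholds, and linkage of laboratory results to the record of attempts. No new patients or procedures are needed. The downside is that the new figure will look less favourable than the per-sample one.
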